9.2. Definition of an Adverse Event (AE)

An AE is any unfavorable and unintended sign, symptom, or disease temporally associated with the use of an investigational medicinal product (IMP) or other protocol-imposed

intervention regardless of attribution. The event does not necessarily have a causal relationship with that treatment or usage.

This includes the following:

- An exacerbation or an unexpected increase in frequency or intensity of a pre-existing condition (other than condition under investigation) including intermittent or episodic conditions.
- Significant or unexpected worsening or exacerbation of the condition/indication under investigation.
- A suspected drug interaction.
- An intercurrent illness.
- Any clinically significant laboratory abnormality.

An AE does not include:

- Anticipated day-to-day fluctuations of any pre-existing conditions including the disease under study.
- Signs and symptoms of the disease under study that do not represent a significant worsening or exacerbation.
- Expected progression of the disease under investigation.

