9.6. Adverse Event Grading and Attribution

All patients must be carefully monitored for AEs, including clinical laboratory tests. AEs should be assessed in terms of their seriousness, intensity, and relationship to the study drug. For consistency, events are to be graded according to the National Cancer Institute Common Terminology Criteria for Adverse Events (CTCAE) version 5.0. A copy of the CTCAE version 5.0 can be downloaded from the CTEP web site:

http://ctep.cancer.gov/protocolDevelopment/electronic_applications/ctc.htm.

If CTCAE criterion does not exist for a particular AE, the investigator should use the grade or adjectives as described below:

- Grade 1: Mild. Does not interfere with patient's usual function.
- Grade 2: Moderate. Interferes to some extent with patient's usual function.
- Grade 3: Severe. Interferes significantly with patient's usual function.
- Grade 4: Life-Threatening. Results in a threat to life or in an incapacitating disability.

The investigator will make a judgment regarding whether or not the AE was related to study drug, as outlined in **Table 5**. For the purpose of safety analyses all AEs that are classified as possibly related will be considered treatment-related events.

Table 5. Criteria for Attribution of Adverse Events

Attribution	Criteria
Not related	The lack of a temporal relationship of the event to study treatment makes a causal relationship not reasonably possible, or other drugs, therapeutic interventions, or underlying conditions provide a sufficient explanation.
Possibly related	The temporal relationship of the event to study treatment makes a causal relationship reasonably possible, and the event is equally explained by exposure to the study treatment than by other drugs, therapeutic interventions, or underlying conditions.

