Design and Sample Size: Based on a study in China, we assume that the event rate is 40% with standard care and that the event rate can be reduced to 15% when Ibrutinib is added to standard care for COVID-19. With 60 patients and using a standard group sequential design, there is 82.8% power to detect a reduction in the event rate under the alternative hypothesis and constraining the one-sided type I error to 20%. Power was calculated using a z-test for the difference in two proportions, pooled variance, and adjustment for small sample sizes with the Casagrande-Pike-Smith correction (EAST v6.5; Cytel, Inc). There will be an interim analysis when 50% of randomized patients have been followed for 30 days from registration. The study will be stopped early if at the interim analysis the observed event rate is higher in the ibrutinib arm (Arm A) than in the control arm (Arm B). We will plan to over-accrue by about 10% for a total accrual goal of 66 patients.

Although the actual reduction in the event rate could be larger than 25%, it could also be as low as 20% and still be quite meaningful. Furthermore, there is uncertainty in the event rate of the control arm. For these reasons, we have incorporated increased flexibility at the time of the interim analysis to potentially increase the sample size if conditional power indicates promising results, and will thus implement an adaptive group sequential design (Chen, DeMets, Lan; 2004).

At the interim analysis, there are 4 possible outcomes: 1) the futility criteria are met and the trial stops early; 2) the conditional power is unfavorable ($<50\%$), and enrollment continues to the planned sample size without an increase in sample size; 3) the conditional power is in a promising zone (defined as conditional power $\geq 50\%$ and $< 82.8\%$), and sample size may be re-estimated with the original sample size updated to boost the power to a target of 82.8%, subject to a maximum sample size of 120; or 4) the conditional power is favorable ($\geq 82.8\%$), and enrollment continues to the planned

sample size without an increase in sample size. When using this procedure, no adjustment to the final test statistic or critical value from the original design is required to control the Type I error rate. In addition, if the conditional power is in the promising zone, we can choose not to increase the sample size beyond what was originally planned or by a flexible amount without penalty.

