Primary Endpoint Analysis: All randomized patients will be included in the primary endpoint analysis and analyzed in the treatment arm to which they were randomized (ITT population). The data will be analyzed using a one-sided Fisher's exact test and a promising signal declared if $p \leq 0.20$ and the event rate is lower in the experimental arm. Since the primary endpoint is to be measured within the first 30 days of registration, we do not expect that primary endpoint information will be missing. However, if there is data missing, the patient will be considered a treatment failure.

Sensitivity analyses include comparison between treatment arm when adjusting for stratification factors and other important variables such as type of cancer or more refined categories of standard of care therapy via logistic regression. If there are events for respiratory failure based on clinical diagnosis without an objective measure and driven solely by resource limitation or if patient has DNI (Do Not Resuscitate) status, a sensitivity analysis will compare arms excluding patients with these events. Sensitivity analyses will be performed for the ITT population and for eligible patients who receive their assigned therapy without a major protocol violation.

Adverse Event Stopping Rules: If there is no concerning safety signal in the lead-in cohort, and the study is able to continue to the randomized component as planned, we have included a plan for comparing toxicity at the interim analyses (first 30 patients across both arms). Accrual will be temporarily suspended to this study and discussion of the data with co-investigators and the data safety monitoring board will occur if we observe adverse events that satisfy the following criteria:

- If the percentage of grade 3/4 all-cause adverse events is at least 15% higher in the ibrutinib arm than in the standard of care arm. This would also include grade 2 hemorrhage if considered significant by the treating physician in collaboration with PI.
- If the percentage of grade 4 all-cause adverse events is at least 15% higher in the ibrutinib arm than in the standard of care arm
- If the percentage of grade 5 treatment-related adverse events is at least 5% higher in the ibrutinib arm than in the standard of care arm

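### No adverse event suspension criterion counts deaths of any cause, so excess deaths called unrelated may meet no numeric rule when the composite endpoint masks them

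*Combined protocol and SAP*

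**What the plan says.** Section 13 (Adverse Event Stopping Rules) sets out a plan for "comparing toxicity at the interim analyses (first 30 patients across both arms"). Accrual pauses for discussion with the co-investigators and the safety board if any of three criteria is met:

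1. "If the percentage of grade 3/4 all-cause adverse events is at least 15% higher in the ibrutinib arm than in the standard of care arm" (clinically significant grade 2 hemorrhage is added to this count);
2. "If the percentage of grade 4 all-cause adverse events is at least 15% higher in the ibrutinib arm than in the standard of care arm";
3. "If the percentage of grade 5 treatment-related adverse events is at least 5% higher in the ibrutinib arm".

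Criteria 1 and 2 ignore attribution; criterion 3 requires it. In Section 9.6 (Table 5) an event is not related if, among other grounds, "underlying conditions provide a sufficient explanation". Section 9.2 excludes from adverse events "Expected progression of the disease under investigation". Section 9.3 requires every death to be reported as a serious adverse event, yet lists COVID-19 progression among things that are not serious adverse events.

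Separately, Section 13 (Design and Sample Size) says: "The study will be stopped early if at the interim analysis the observed event rate is higher in the ibrutinib arm". That event is respiratory failure or in-hospital death within 30 days of registration, with no attribution test.

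**The concern.** The two less severe categories are compared whatever the cause, while the most severe depends on a judgment in each case. In hospitalized COVID-19 patients with cancer, the underlying illness can explain almost any death. Section 4.5 names impaired immune response to the virus, cardiac toxicity overlapping with viral cardiac symptoms, and secondary infection as concerns. Harm of this kind may look like the disease in a single patient and show only as a difference between arms in deaths of any cause. No suspension criterion makes that comparison.

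At stake is whether a mortality imbalance in the first 30 randomized patients is certain to prompt a pause and review, or does so only if it also moves the composite or someone chooses to act.

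**Working it through.** **Inputs.** From Section 13: 1:1 randomization and a look at the first 30 patients, so about 15 per arm; thresholds of 15, 15 and 5, read as percentage points; 40% control event rate. The documents do not split that 40% into deaths and non-fatal failures, so every split below is an assumption.

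**Step 1: the plan's own figures.** The probability that the interim stop fires is the exact binomial sum

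P(A − B ≥ d) = Σ Bin(a; 15, pA) × Bin(b; 15, pB) over a − b ≥ d, with d = 1.

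For Scenarios 1 to 4 this gives 3.5%, 5.0%, 7.7% and 9.2%; the table has 3.5%, 5.0%, 8.0% and 9.0%. The stated power also reproduces. The corrected n per arm is 30 × (1 − 1/(30 × 0.25))² = 22.5, and P(interim Z > 0 and final Z > 0.842) at information fraction 0.5 is 82.8%. So the interim stop is an active rule that fires on any observed excess of the composite.

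**Step 2: thresholds in patients.** 0.15 × 15 = 2.25, so criteria 1 and 2 need at least 3 excess patients (20 points). 0.05 × 15 = 0.75, so criterion 3 needs 1 excess related death (6.7 points).

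**Step 3: a case that meets no rule.**

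| | Ibrutinib | Control |
|---|---|---|
| Deaths, all called unrelated | 5 | 1 |
| Non-fatal respiratory failure | 1 | 6 |
| Composite | 6/15 (40.0%) | 7/15 (46.7%) |
| Related deaths (criterion 3) | 0 | 0 |

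Deaths differ by 4/15 (26.7 points), but the composite favors ibrutinib, so the interim stop does not fire. Criterion 3 sees 0 versus 0. Criteria 1 and 2 respond only if non-fatal grade 3/4 events happen to differ as well.

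**Step 4: how often the composite stop misses it.** Multinomial model, 15 per arm, control 10% deaths plus 30% non-fatal failure:

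| Ibrutinib deaths + non-fatal failure | Stop fires | At least 3 excess deaths and no stop |
|---|---|---|
| 30% + 30% (no offset) | 82% | 5% |
| 30% + 10% (same composite) | 43% | 24% |
| 30% + 0% | 22% | 38% |

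With no offset and deaths of 5/15 versus 1/15, the stop fires 91% to 93% of the time for non-fatal failure of 10% to 30% in both arms.

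**Step 5: criteria 1 and 2 depend on an unstated counting rule.** Assume deaths of 5/15 versus 1/15, and that non-fatal grade 3/4 events affect a further 30% of each arm (grade 4: 15%). The chance that the criterion fires depends on the share of dying patients who also count:

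| Share of deaths also counted | Criterion 1 | Criterion 2 |
|---|---|---|
| None | 16% | 10% |
| Half | 43% | 42% |
| All | 72% | 73% |

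Section 13 does not say whether a patient whose event becomes fatal stays in the grade 3/4 or grade 4 count.

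**Step 6: a separate all-cause death criterion.** The same binomial sum on deaths alone:

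| True mortality (ibrutinib vs control) | 15-point threshold (≥3 deaths) | 5-point threshold (≥1 death) |
|---|---|---|
| 10% vs 10% | 6.1% | 37.5% |
| 20% vs 20% | 12.5% | 40.9% |
| 30% vs 10% | 59.2% | 88.3% |

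At 5/15 versus 1/15 the 15-point threshold fires 77% of the time.

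**The case against.** A reader might infer that an excess of COVID-19 deaths on ibrutinib triggers nothing. The documents do not support that. In-hospital deaths by day 30 count in the composite without attribution, one excess composite event is enough, and the consequence is stopping the trial, not a pause. With no offset, that rule fires more often than a 15-point death criterion would (82% against 59% at 30% versus 10% deaths). Under Section 9.9 the monitoring committee reviews all serious adverse events in real time, may receive a summary of deaths, reviews efficacy data and can recommend suspension. Section 13 lets the study team suspend accrual when no criterion is met.

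This limits the gap but does not close it. The composite gives death the same weight as high-flow oxygen, and it covers only in-hospital events by day 30. Committee review and discretionary suspension have no stated between-arm threshold.

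A reader might also infer that a grade 4 event that turns fatal drops out of criteria 1 and 2. The text does not say so; it is silent, and Step 5 shows how much depends on the answer.

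Finally, simply widening criterion 1 to grades 3 to 5 would not be enough. If non-fatal respiratory failures count as adverse events, the widened criterion is another composite. With the Step 3 proportions as true rates (6/15 versus 7/15), it fires about 10% of the time.

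**Conclusion.** The point holds in a limited form. The suspension criteria contain no comparison of deaths of any cause. Excess deaths called unrelated meet none of them unless the dying patients also have counted grade 3/4 events. The composite stop catches most unmasked excesses. No numeric rule is sure to respond when the excess is offset by fewer non-fatal failures, or when deaths occur after discharge or after day 30.

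The size depends on the assumed split: from 5% of trials with at least 3 excess deaths and no stop (no offset), through 24% (equal composites), to 38% (no non-fatal failure on ibrutinib). These figures assume 15 per arm and 10% control deaths. The gap itself follows from the wording and needs none of these assumptions.

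**What to change.** Add a fourth criterion to the Section 13 list: the percentage of patients who have died from any cause, whatever the attribution and whether or not in hospital, is at least 15 percentage points higher on ibrutinib at the interim data cut. The action is the same temporary pause and data review. Keep criterion 3. A 5-point threshold is not advisable, because a single excess death would meet it.

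State also that:
- criteria 1 and 2 count grade 3 or higher and grade 4 or higher, so that a fatal event stays in both counts;
- the exclusions of COVID-19 progression in Sections 9.2 and 9.3 do not remove deaths from these comparisons, and the two statements on deaths and progression in Section 9.3 are reconciled.

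The cost is a few lines of text and a modest rise in the chance of a pause. The new criterion adds at most about 6 percentage points at 10% mortality in both arms, or 12 at 20%. With 7% deaths in both arms, all counted, false alarms rise from 15.9% to 17.2% for criterion 1 (30% to 37% per arm) and from 9.7% to 13.3% for criterion 2 (15% to 22%). Like the existing criteria, this is a single look; deaths after the interim cut remain a matter for committee review.

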1. PROTOCOL SYNOPSIS

IND Sponsor	The Ohio State University
Protocol Title	Randomized Double-Blind Phase 2 Trial of Ibrutinib versus Standard Treatment for COVID-19 Illness Requiring Hospitalization with Safety Lead-In
Protocol Number	Protocol
Phase of Development	Phase 2 Randomized Adaptive Trial
Rationale	
The SARS-CoV-2 virus, a novel coronavirus represents a serious human to human pathogenic virus and represents a current WHO pandemic pathogen. The clinical syndrome manifested by SARS-CoV-2 is termed COVID-19 with a common presentation of fever (89%), cough (68%), CT abnormalities (86%) and lymphocytopenia (84%) with nausea (5%) and diarrhea (4%) being uncommon. Severe disease that requires admission occurs in 20% and a subset of these patients require ICU care (6%), intubation (2.3%) or die (1.4%). The death rate from COVID-19 in different populations has ranged from 2.4% in China to 7.2% in Italy. Death rate from COVID-19 increases proportionally with older age, being highest among older patients and also those who are immunocompromised or have other co-morbidities or lymphocytopenia. Among hospitalized cancer patients with COVID-19 in China, a 38% frequency of mechanical ventilation or death occurred compared to 8% among patients without cancer. The systemic and pulmonary pathogenesis derived from clinical cases of ICU hospitalized COVID-19 cases and autopsy series demonstrate increased levels of plasma inflammatory cytokines including TNF-alpha, IL-6, and IL-2, and IL-10 and neutrophilic infiltration, macrophages, monocytes, minimal lymphocytes (CD4+ T-cells predominantly) and type 2 pneumocytes with viral particles. Other risk factors for severe COVID-19 illness is the presence of neutrophilia, organ dysfunction (elevated LDH), coagulation abnormalities, thrombocytopenia, and lymphocytopenia suggesting both findings observed in hemophagocytic syndrome, and immune deficiency.
 
To date, there have been no studies published that follow immune response serially in patients with SARS-CoV-2 infection and COVID-19 syndrome. Several studies have demonstrated cross comparative studies of moderate versus severe COVID-19 syndrome where differential decline in CD4 and CD8 cells occurs with increasing features of both exhausted T-cells (increased PD1, LAG3, CTLA4, and decreased intracellular gamma-interferon) and inflammatory cytokines. These findings mimic other chronic virus and parasitic infections where inability of CD4 T-cells to generate cytotoxic gamma-interferon and T-

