2.2 Secondary Objectives

- To determine time to clinical resolution of need for supplemental oxygen (i.e. maintenance of oxygen saturation of 93% or greater on room air with ambulation) or need for supplemental oxygen above baseline for those on home oxygen.
- To determine rate of ICU admission and length of ICU admission for patients treated with ibrutinib (Arm A) versus control population receiving standard therapy (Arm B)
- To determine rate of shock requiring vasopressor support for patients treated with ibrutinib (Arm A) versus control population receiving standard therapy (Arm B)
- To determine the rate of secondary infection (bacterial, fungal, viral) for patients treated with ibrutinib (Arm A) versus control population receiving standard therapy (Arm B)
- To determine the time to hospital discharge for patients treated with ibrutinib (Arm A) versus control population receiving standard therapy (Arm B)
- To determine grade 3 or higher toxicity observed in patients treated with ibrutinib (Arm A) versus control population receiving standard therapy (Arm B)
- To determine time to mechanical ventilation, the number of days of mechanical ventilation per patient and total observed in patients treated with ibrutinib (Arm A) versus control population receiving standard therapy (Arm B)
- To determine the overall survival at 3 and 12 months post-enrollment.

Exploratory Objectives

- To determine the time to defervescence (oral temperature<100.5 degrees F for a 48 hour time period) among patients treated with ibrutinib (Arm A) versus control population receiving standardtherapy (Arm B)
- To examine the impact of baseline clinical features (e.g. type of cancer, active therapy), duration of symptoms prior to admission and laboratory features (e.g. T cell count) on outcome for patients treated on this therapeutic study
- To determine the proportion of patients with viral clearance at end of ibrutinib therapy, time of hospital discharge and follow up thereafter among patients treated with ibrutinib (Arm A) versus control (Arm B) treatment
- To determine the time and proportion of patients who develop IgM and IgG levels toward SARS-CoV-2 treated with ibrutinib (Arm A) versus control treatment (Arm B)
- To examine immune cell subsets for absolute number, activation, exhaustion markers, and presence of maturation arrest (NK cells) at baseline and over time among patients treated with ibrutinib (Arm A) versus control (Arm B) treatment

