3.1. Primary Endpoints

Proportion of patients who develop respiratory failure (as defined elsewhere in the protocol) or death during hospitalization for COVID-19 infection within 30 days of registration

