4. BACKGROUND

4.1 SARS-CoV-2 and COVID-19:

The SARS-CoV-2 virus, a novel coronavirus originated from Wuhan China and represents a serious human to human pathogenic virus. SARS-CoV-2 has a variable phenotype ranging from asymptomatic carrier state to rapidly progressive acute respiratory distress syndrome. The clinical syndrome manifested by SARS-CoV-2 is termed COVID-19. Both the infectiveness and pathogenic nature of this respiratory droplet transmitted RNA virus greatly exceeds that of influenza, likely as a consequence of no prior human exposure or available vaccine. SARS-CoV-2 has rapidly spread throughout the world and was recently by the WHO as a pandemic pathogen. Notably, SARS-CoV-2 has common presentation of fever (89%), cough (68%), CT abnormalities (86%) and lymphocytopenia (84%) with nausea (5%) and diarrhea (4%) being uncommon. Severe disease that requires admission occurs in 20% and a subset of these patients require ICU care (6%), intubation (2.3%) or die (1.4%).¹ The death rate from COVID-19 in different populations has been different from China (updated data, 2.4%) to Italy (7.2%).^{2,3} Death rate from COVID-19 increases proportionately with older age, being highest among older patients and also those who are immunocompromised or have other co-morbidities or lymphocytopenia ^{1,3-5}. Among hospitalized cancer patients with COVID-19 in China, a 38% frequency of mechanical ventilation or death occurred compared to 8% among patients without cancer⁶. The systemic and pulmonary pathogenesis derived from clinical cases of ICU hospitalized COVID-19 cases and autopsy series demonstrates increased levels of plasma inflammatory cytokines including TNF-alpha, IL-6, and IL-2, and IL-10 and neutrophilic infiltration, macrophages, monocytes, minimal lymphocytes (CD4+ T-cells predominately) and type 2 pneumocytes with EM viral particles.^{7,8} Other risk factors for severe COVID-19 illness include the presence of neutrophilia, organ dysfunction (elevated LDH), coagulation abnormalities, thrombocytopenia, and lymphocytopenia suggesting both findings observed in hemophagocytic syndrome that often accompanies immune deficiency and dysregulation ^{1,9,10}.

4.2 Immune Response to SARS-CoV-2:

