We note that the above stopping rules may be adjusted at any time during the conduct of the trial and in consideration of newly acquired information regarding the adverse event profile of the treatment(s) under investigation. The study team may choose to suspend

accrual because of unexpected adverse event profiles that have not met the specified rules above.

Secondary Endpoints: At the final analysis, all adverse events will be summarized by grade, type, and attribution (regardless of attribution and treatment-related) for each arm. Time-to-event endpoints such as time to discharge and overall survival will be estimated for each arm using the method of Kaplan-Meier. Medians estimates and/or estimates at specific time points will be provided with 95% confidence intervals. The proportion of patients with viral clearance at the time of hospital discharge will be estimated with 95% confidence intervals for each arm. For all biomarkers, descriptive statistics (e.g., means, medians, standard deviations, interquartile range) and graphical displays will be used to characterize central tendency and variability over time. Values will be log transformed as appropriate to reflect biologic plausibility. We will evaluate for statistical trends over time among the biologic measurements, with multiple measurements per patient, using mixed effects models. Lastly, associations between baseline characteristics and the primary endpoint will be evaluated with logistic regression, adjusting for arm. These analyses will be largely descriptive, as a result of a limited sample size.

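### Time to discharge is planned as Kaplan-Meier with no rule for in-hospital deaths; if deaths are censored, the percentage discharged is overstated

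*Combined protocol and SAP*

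**What the plan says.** Section 13, Secondary Endpoints, states: "Time-to-event endpoints such as time to discharge and overall survival will be estimated for each arm using the method of Kaplan-Meier". It continues: "Medians estimates and/or estimates at specific time points will be provided with 95% confidence intervals". It fixes no time point for discharge, describes no between-arm test for it, and calls these analyses mostly descriptive because the sample is small.

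Section 2.2 states time to hospital discharge as a comparison of Arm A with Arm B. Section 3.2 lists the matching endpoint as the duration of hospitalization. Neither says how a patient who dies before discharge is counted. There is no censoring rule for this endpoint, and competing risks and cumulative incidence are not mentioned.

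In-hospital death is an expected outcome. The primary endpoint in Section 3.1 is respiratory failure "or death during hospitalization for COVID-19 infection within 30 days of registration". Sections 7.7 and 7.8 end follow-up at death and take the patient off study. Those are conduct rules, not analysis rules.

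**The concern.** Kaplan-Meier is right for overall survival, where death is the event. For discharge alive, death makes the event impossible. Censoring a patient at death treats that patient as someone who could still be discharged later, at the same rate as those remaining in hospital. One minus Kaplan-Meier then estimates the percentage who would be discharged if nobody could die. That is higher than the percentage actually discharged whenever some discharges follow a death.

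The objective compares the arms. The size of the error depends on how many patients die and when, so it can differ between arms. A benefit that comes through fewer deaths could then be partly or wholly absent from the discharge curves.

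**Working it through.** The plan states no figure for time to discharge, so there is none to reproduce. The check measures the gap between the two estimators.

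**Inputs from the documents**
- Deaths: 1.4% (Synopsis, Rationale; Section 4.1), and 2.4% and 7.2% (same places). These describe broader populations than hospitalised cancer patients. The closer figures, 38% ventilation or death (Section 4.1) and 40% respiratory failure or death in controls (Section 13), do not separate out death.
- Arm size: "We will plan to over-accrue by about 10% for a total accrual goal of 66 patients", so 66/2 = 33 per arm. The increase is "subject to a maximum sample size of 120", so at most 120/2 = 60 per arm.

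**Assumptions:** deaths censored at death; constant discharge hazard d = 0.05, 0.08 or 0.12 per day; day 30 as the time point; death proportions of 5, 10 and 20% by day 30.

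**Formulas.** With death hazard m and T = 30:
- Deaths by day 30: p = m/(d+m) × [1 − exp(−T(d+m))], solved for m.
- Kaplan-Meier, deaths censored: 1 − exp(−Td).
- Aalen-Johansen: d/(d+m) × [1 − exp(−T(d+m))].

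Example, d = 0.08 and p = 10%: m = 0.00962. Kaplan-Meier gives 1 − exp(−2.4) = 90.9%. Aalen-Johansen gives 0.08/0.08962 × [1 − exp(−2.689)] = 83.2%. The overestimate is 7.7 points.

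| Deaths by day 30 | d = 0.05 | d = 0.08 | d = 0.12 |
|---|---|---|---|
| Kaplan-Meier, any p | 77.7% | 90.9% | 97.3% |
| 1.4%: overestimate | 0.8 | 1.1 | 1.3 |
| 2.4% | 1.4 | 1.8 | 2.2 |
| 7.2% | 4.2 | 5.5 | 6.5 |
| 5% (assumed) | 2.9 | 3.8 | 4.5 |
| 10% (assumed) | 5.8 | 7.7 | 9.1 |
| 20% (assumed) | 11.8 | 15.7 | 18.4 |
| Median shift at 5/10/20%, days | 0.4/0.9/2.3 | 0.2/0.5/1.2 | 0.1/0.3/0.8 |

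Simulation with 33 patients and 10% deaths gives mean overestimates of 5.9, 7.8 and 9.0 points (5,000 runs), in line with the 10% row.

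**A second parameterisation.** Fix 10% still in hospital at day 30, with F discharged and p dead. Kaplan-Meier is then 1 − 0.10^(F/(F+p)). At p = 5, 10 and 20%, F is 85, 80 and 70%, and Kaplan-Meier gives 88.6, 87.1 and 83.3%. The overestimates are 3.6, 7.1 and 13.3 points.

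**Timing of deaths (d = 0.08).** If the death hazard m acts only from day t0 to day t1, deaths are exp(−d·t0) × m/(m+d) × [1 − exp(−(m+d)(t1−t0))].

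| Deaths | Window, days | m | Aalen-Johansen | Overestimate |
|---|---|---|---|---|
| 10% | 0–7 | 0.0199 | 82.1% | 8.8 |
| 10% | 7–14 | 0.0366 | 83.0% | 8.0 |
| 10% | 14–30 | 0.0441 | 85.5% | 5.4 |
| 15% | 14–30 | 0.0795 | 82.5% | 8.5 |

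Late deaths of 15% give a smaller error than early deaths of 10%, so the arm with more deaths need not have the larger error.

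**Between arms, assumed 10% v 20% deaths.** With equal discharge hazards, true day-30 discharge differs by 6.0, 8.0 and 9.3 points at d = 0.05, 0.08 and 0.12, and Kaplan-Meier shows no difference. In the second parameterisation the true difference is 80 − 70 = 10 points and Kaplan-Meier shows 87.1 − 83.3 = 3.8. The 95% half-width for the true difference in the first case, 1.96 × √[a(1−a)/n + b(1−b)/n], is 22.3, 19.5 and 17.8 points at 33 per arm, and 16.5, 14.4 and 13.2 at 60 per arm.

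**The case against.** The strongest reply is that the plan is silent rather than shown to be wrong. Kaplan-Meier can be run without this bias by keeping patients who die in the risk set as not discharged up to a fixed horizon. That stands, which is why the conclusion is conditional. But censoring at death is the ordinary use of the named method, and ending follow-up at death points the same way.

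The plan could also be met by reporting medians alone. Those move by 0.9 days or less at 5 to 10% deaths, against a simulated 95% sampling range of about 5 to 15 days (33 patients, d = 0.08, 10% deaths). That also stands. The bias matters for time-point estimates, which the plan allows but does not require.

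The discharge hazards, the higher death rates and the timing windows are all assumed, so the size in this trial is unknown. Complete masking of an arm difference follows from assuming equal discharge hazards and should not be read as typical. The hidden difference is smaller than sampling error throughout, no decision depends on it, and deaths are visible in overall survival and the primary composite. All of this limits the priority. It does not remove a systematic error with a known direction, and a confidence interval around the wrong quantity does not warn the reader.

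**Conclusion.** The concern holds, at low priority. Section 13 names Kaplan-Meier for discharge and gives no rule for in-hospital deaths. If those deaths are censored at death, the percentage discharged is overstated. At 5 to 20% deaths by day 30, the assumed hazards put the excess between 2.9 and 18.4 points. At the broader-population rates the documents cite it is 0.8 to 6.5 points, which does not calibrate it for hospitalised cancer patients. The effect on medians is small. The primary Fisher test, type I error, power and interim rules are unaffected.

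**What to change.** Keep Kaplan-Meier for overall survival. For time to discharge, add to Section 13, for example:

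> Death in hospital is a competing event for discharge alive. The Aalen-Johansen cumulative incidence of discharge alive will be reported by arm with 95% confidence intervals.

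Holding patients who die in the risk set as not discharged to a fixed horizon gives the same estimate when follow-up to that horizon is otherwise complete. The planned medians and time-point estimates can stay, read from the cumulative incidence curve.

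State the same death rule for any other non-fatal endpoint in Section 3.2 that is analysed as time-to-event, such as time to ICU admission, mechanical ventilation, clinical resolution or viral clearance.

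The cost is one or two sentences. It uses standard software and data already collected, with no change to sample size or the primary analysis. Fixing the rule now also avoids choosing it after the deaths are known.
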